10.2.9. Time to AML Progression

Time to AML Progression is defined as the time from the date of randomization until the date the subject has documented progression to AML. For subjects who have progression to AML documented in central lab report, the earliest sample collection date with the diagnosis of “s-AML arising from previous MDS” will be used as the date to AML progression (in case multiple records are available for the samples collected on the same day, the records with the latest report date will be used). For subjects who only have progression to AML documented in the Follow-up Status CRF, the date of progression from the CRF page will be used. Subjects who do not progress to AML will be censored at the date of last follow-up or at date of death. Time to AML progression curves will be estimated using KM methods and treatment groups will be compared using a log-rank test. KM estimates for median time to AML progression and the 1-year and 2-year AML progression rate will be summarized for each treatment group. A Cox proportional hazards model will be used to estimate the corresponding hazard ratio and 95% CI. A competing risk analysis, treating death as a competing risk for AML progression, will be conducted for exploratory purposes.

10.2.10. Erythroid response (HI-E)

HI-E is defined according to IWG 2006 criteria ([Appendix E](#)). HI-E response will be analyzed similarly as HI-P (Section [10.2.2](#)). The response collected in the IWG MDS Response Criteria CRF, and the response derived using central labs per IWG criteria will be summarized separately. The detailed derivation is provided in [Appendix F](#).

10.2.11. Duration of RBC transfusion reduction

A subject will be considered as a RBC transfusion reduction responder if the subject has at least 4 units reduction in transfusion units over any consecutive 56 days period compared to the baseline transfusion units in 56 days. Subjects with less than 4 units RBC transfusions during the 56 days immediately preceding randomization will not be considered as a RBC transfusion reduction responder. The duration of response will only be determined for RBC transfusion reduction responders. Subjects who maintain the response through the end of the treatment period or who are still on-going with the treatment will be censored at the end date of evaluation period which is defined in Section [10.1](#). The derivation for responder and the calculation of the duration are similar as for the RBC transfusion independence described in Section [10.1](#) and Section [10.2.4](#). Duration of RBC transfusion reduction response will be analyzed descriptively using KM methods for the RBC transfusion reduction responders.

10.2.12. Platelet transfusion independence

Platelet transfusion independence is defined as the absence of any platelet transfusion during any consecutive “rolling” 56 days during the treatment period, (ie, Day 1 to 56, Day 2 to 57, Days 3 to 58, etc.). Subjects will be considered platelet transfusion dependent at baseline if they have received ≥ 2 platelet transfusions during the 56 days immediately preceding randomization and had no consecutive 28-day period during which no platelet transfusions were administered. The response is derived similarly as the derivation of the primary efficacy endpoint, except using platelet transfusion. Frequency cross-tabulations of platelet transfusion status (dependent or independent) at baseline versus on treatment will be presented by treatment group.

10.2.13. Duration of platelet transfusion independence

Duration of platelet transfusion independence will be analyzed only for subjects who are platelet transfusion dependent at baseline and achieve platelet transfusion independence on treatment. The calculation of the duration is similar as for the duration of RBC transfusion independence of ≥ 56 days (Section [10.2.4](#)), except using platelet transfusion. Duration of platelet transfusion independence will be analyzed descriptively using KM methods.

10.2.14. Time to platelet transfusion independence

Time to platelet transfusion independence is defined as the time between randomization and the first documented date of onset of transfusion independence (ie, Day 1 of 56 without any platelet transfusions). The derivation is similar as for the time to RBC transfusion independence of ≥ 56 days (Section [10.2.5](#)), except using platelet transfusion. Subjects who are platelet transfusion independent at baseline will be excluded from the analysis. Time to platelet transfusion independence will be analyzed descriptively using KM methods. Time to platelet transfusion

independence (in month) for at least 56 days will also be summarized using descriptive statistics based on subjects who achieve the response.

10.2.15. Hematologic response

Hematologic response (Complete Remission [CR], Partial Remission [PR], Marrow CR [mCR], Stable Disease [SD], Disease Progression [PD], Failure, Relapse after CR or PR, and Cytogenetic Response) is defined according to IWG 2006 criteria ([Appendix E](#)). Subjects will be classified according to their best response achieved during treatment for the response categories of CR, PR, mCR, SD, PD, and failure. Only subjects who achieve CR or PR will be included in the Relapse after CR or PR category. Subjects will be evaluated for cytogenetic response regardless of their response status in other categories. For cytogenetic response, subjects will be classified as having a complete or partial response based on the best response achieved during treatment. Hematologic response will be presented descriptively, by treatment group, using counts and percent. All above responses collected in the IWG MDS Response Criteria CRF will be summarized. In addition, hematologic response CR, PR, SD, mCR, relapse after CR or PR, cytogenetic response, and hematologic improvement will be derived using central labs per IWG criteria and will be summarized separately. The detailed derivation is provided in [Appendix F](#).

10.2.16. Clinically significant bleeding event

Clinically significant bleeding event is defined as: any intracranial or retroperitoneal bleed; bleeding requiring transfusions of > 2 units of blood/blood products; bleeding associated with a decrease in hemoglobin of > 2 g/dL; or bleeding from any site requiring transfusions of > 2 units of blood. Number and percentage of subjects experiencing a clinically significant bleeding event will be presented by treatment group. Additionally, the number and percentage of subjects by the number of clinically significant bleeding events experienced during the treatment period will be summarized by treatment group.

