6.7.2 Assessment of Bleeding Events

An assessment of all bleeding events during the treatment phase should be performed weekly on Day 1, 8, 15 and 22 of Cycles 1-2, biweekly on Day 1 and 15 of Cycles 3-12, and on Day 1 of each treatment cycle thereafter and at Treatment Discontinuation. Information for each bleeding event should be recorded on the appropriate CRF.

The investigative site may inquire about signs and symptoms of bleeding events via a phone call made to the subject. All phone calls made to the subject should be performed by a medically-qualified person (eg, principal investigator or sub-investigator) at the investigative site and adequately documented in the subject's medical record.

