10.1 Overview

This phase 3, multicenter, randomized, double-blind, placebo-controlled, parallel-group study is designed to compare the efficacy and safety of oral azacitidine plus best supportive care versus placebo plus best supportive care in subjects with RBC transfusion-dependent anemia and thrombocytopenia (platelet count $\leq 75 \times 10^9/L$) due to IPSS lower-risk MDS.

All data will be summarized by treatment group. In addition, where appropriate, a total column will be included to summarize subjects across treatment groups. Summaries of continuous variables will present the number of subjects included in the analysis (N), the mean and standard deviation (SDev) of the mean, the median, the minimum, and the maximum statistics. Counts and percentages will be presented in summaries of categorical variables. The denominator for each percentage will be the number of subjects in the population treatment group unless otherwise specified. In general, missing data will not be imputed unless otherwise specified.

All statistical analyses specified in this protocol will be conducted using SAS[®] Version 9.2 or higher unless otherwise specified.

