4.4. Sample Size

The basis for the power and sample size determination will be a test of the equality of the overall survival curves between the oral azacitidine and placebo treatment groups using a stratified log-rank test. Assuming a median OS of 18 months in the placebo treated group ([Garcia-Manero, 2008a](#)), which takes into account possible cross-over outside of the protocol of placebo treated

subjects to active treatment during the observation period, and a median OS of 25.7 months (43% improvement) in the oral azacitidine treated group, 216 subjects (108 in each group) would have approximately 72% power to detect a constant hazard rate ratio of 0.70 using a two-sided log rank test with overall significance level of 0.05. It is assumed that the OS distribution is exponential with a constant failure (hazard) rate and that accrual is uniform during the accrual period (56 months) with an overall drop-out rate of 5% from both treatment groups. Full information necessary for a log rank test to have 72% power will be achieved when approximately 205 deaths have occurred in both treatment groups, which is expected approximately 134 months after randomization of the first subject into the study.

An interim analysis of the OS endpoint will be performed and reported when all subjects have completed 12 months [52 weeks (364 days)] of double-blind treatment or have been discontinued from treatment (see Section 15).

While 56 days (8 weeks) is the standard response criteria for hematologic improvement (IWG 2006 criteria; Cheson, 2006; Appendix E), limited information is available on the target population for estimating the response rate for the primary endpoint of RBC transfusion independence maintained for ≥ 84 days (12 weeks).

A total sample size of 216 subjects (108 in the active treatment group and 108 in the placebo group) will have approximately 99% power to detect the difference between a response rate of 0.30 in the active treatment group and a response rate of 0.05 in the placebo group, and approximately 70% power to detect the difference between a response rate of 0.15 in the active treatment group and a response rate of 0.05 in the placebo group. The power calculations for response rate are based on a two-sided alpha of 0.05 and test statistics on the difference of proportions using an un-pooled estimate of variance.

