10. EFFICACY ANALYSIS

All efficacy analysis will be performed on the ITT population. Key efficacy analysis will be performed on the mITT population as supportive evidence and to assess the robustness of the efficacy findings. Subjects will be analyzed according to randomized treatment group.

A sequential gate-keeping approach will be used to control the overall type I error rate and to perform hypothesis testing on multiple endpoints. Two endpoints, the primary efficacy endpoint of RBC transfusion independence and the key secondary endpoint of OS, will be tested sequentially in the pre-specified order. The primary efficacy endpoint will be tested first at the two-sided 0.05 significance level. In order to preserve the overall alpha level at 0.05 across the RBC transfusion independence and OS endpoints, formal statistical inference for the OS analyses can only be made if superiority of oral azacitidine is demonstrated for the primary efficacy endpoint, RBC transfusion independence, at the two-sided 0.05 significance level.

The primary efficacy endpoint, RBC transfusion independence, will be analyzed and reported only once after all 100% of the information is available for RBC transfusion independence rates (ie, after all 216 subjects have completed 12 months (52 weeks [364 days]) of double-blind treatment or have been discontinued from treatment). An interim analysis of the OS endpoint will also be conducted at the time of the analysis of the primary efficacy endpoint as the number of required 205 death events will not be reached by the time of the final analysis for the RBC transfusion independence endpoint. An O'Brien-Fleming group sequential type boundary will be used to preserve the overall alpha level of 0.05 for the analysis of OS.

The remaining secondary efficacy variables, with the exception of the proportion of subjects progressing to AML and time to AML progression, will be analyzed and reported once at the time of the analysis of RBC transfusion independence. Subjects will continue to be followed for progression to AML and survival until 205 deaths have been observed. Other than the pre-specified sequential testing of RBC transfusion independence and OS, no additional alpha adjustments for multiplicity will be made.

As there were no subjects enrolled from Japanese sites, the randomization stratification factor "country of enrollment (ie, Japan versus ROW)" will not be used when the analysis is performed.

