Additionally, the exposure-adjusted incidence rate (EAIR) per 100 person-years will be summarized for all TEAEs and Grade 3 or 4 TEAEs by system organ class, preferred term, and treatment group. The EAIR per 100 person-years is defined as $100 \cdot (n/T)$, where n is the number of subjects with the specific AE at the SOC or PT level, and T is total exposure time (in years) among subjects included in the analysis. Subjects with multiple occurrences of the specific event will be counted only once in the numerator. The exposure time for a subject without the specific event is the treatment duration (calculated as $\text{Min}[\text{death date, last dose date} + 28] - \text{first dose date} + 1$ day), whereas the exposure time for a subject with the specific event is the treatment duration up to the start date (inclusive) of the first occurrence of the specific event. The total exposure time in years is calculated by dividing the sum of exposure time in days over all subjects included in the analysis by 365.25. The EAIR per 100 person-years is interpreted as the expected number of subjects with at least one occurrence of the specific event per 100 person-years of exposure to the study drug.

Listings for the corresponding summary tables for TEAE, Serious TEAE, TEAEs leading to study drug discontinuation and TEAEs leading to death will be presented separately.

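### Clinically significant bleeding is summarised only as a crude percentage over each subject's own open-ended treatment period, so unequal time on treatment would distort the comparison between arms in either direction.

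*SAP*

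**What the plan says.** The proportion of subjects with a clinically significant bleed is a listed secondary endpoint (Protocol 3.2, SAP 4.2). The analysis in SAP 10.2.16, which matches Protocol 10.6.2.2, has two parts. The first is "Number and percentage of subjects experiencing a clinically significant bleeding event will be presented by treatment group". The second is a tabulation of subjects by how many "clinically significant bleeding events experienced during the treatment period will be summarized by treatment group". SAP section 16 lists no change on this point.

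The denominator is subjects, not time. Protocol 10.1 states: "The denominator for each percentage will be the number of subjects in the population treatment group unless otherwise specified". The population is ITT, since SAP section 10 states: "All efficacy analysis will be performed on the ITT population".

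Observation follows treatment. Protocol 6.7.2 states: "An assessment of all bleeding events during the treatment phase should be performed weekly on Day 1, 8, 15 and 22 of Cycles 1-2". Assessment then falls to every other week in Cycles 3 to 12, to once per cycle after that, and ends at the Treatment Discontinuation visit. Protocol Table 1 schedules no bleeding assessment in follow-up.

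Treatment length is open. Under Protocol 8.2 subjects may stay on treatment while they benefit. Under Protocol 6.7.6 they stop at the end of Cycle 6 if no continuation criterion is met. Under Protocol section 12 they may stop for adverse events, progression, lack of efficacy or death.

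The SAP does allow for time elsewhere. In SAP 11.1, "the exposure-adjusted incidence rate (EAIR) per 100 person-years will be summarized for all TEAEs", and the same is done for Grade 3 or 4 events. SAP 11.1.2 plans an exposure-adjusted table for the special-interest categories, which include hemorrhagic events. SAP 13 gives hospitalization rates per person-year.

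**The concern.** A percentage of subjects with an event compares risk fairly only if the arms are watched for about the same time. Here, watching stops when treatment stops, and treatment stops for reasons linked to outcome. A subject who leaves early, or is randomized and never dosed, stays in the ITT denominator as event-free with little or no assessed time. Two arms with the same bleeding rate would then show different percentages and different event counts. Two arms with different rates could show the same percentage.

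Bleeding matters clinically in this population: platelet counts at entry are at or below 75 x 10^9/L, and Protocol 1.4.1 lists thrombocytopenia among the known risks of oral azacitidine. What is at stake is how the by-arm bleeding table is read. No confirmatory error rate is involved.

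**Working it through.** **Plan's own figure.** There is none. The documents state no expected bleeding rate, no expected proportion and no exposure by arm. Everything below except the arm size is assumed and illustrates the mechanism.

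**Inputs.**
- Arm size: "216 subjects (108 in each group) would have" the stated power (SAP 4.4), so 108 per arm.
- Assumed bleeding hazard h: 0.3 and 0.6 per year, the same in both arms and constant over time.
- Assumed treatment time: exponential, with medians of 4, 6 or 8 months.

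**Formulas.** The stopping rate is s = ln 2 / median. The chance of a first bleed before stopping is h / (h + s). The expected at-risk time up to first bleed or stopping is 1 / (h + s).

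**Stopping rates per year.** 4 months: 0.6931 / 0.3333 = 2.079. 6 months: 0.6931 / 0.5 = 1.386. 8 months: 0.6931 / 0.6667 = 1.040.

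**Crude proportions at equal hazard.**

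| h per year | Median 4 months | Median 6 months | Median 8 months | Ratio 4 vs 6 | Ratio 4 vs 8 |
|---|---|---|---|---|---|
| 0.3 | 0.3/2.379 = 12.6% | 0.3/1.686 = 17.8% | 0.3/1.340 = 22.4% | 0.71 | 0.56 |
| 0.6 | 0.6/2.679 = 22.4% | 0.6/1.986 = 30.2% | 0.6/1.640 = 36.6% | 0.74 | 0.61 |

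The true ratio is 1.0 throughout. For 4 versus 6 months with 108 per arm, this is about 14 versus 19 subjects at h = 0.3 and about 24 versus 33 at h = 0.6.

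**Equal or reversed exposure.** With equal medians the proportions are equal and nothing is distorted. If the placebo arm is the shorter one, the ratios invert: 17.8/12.6 = 1.41 and 30.2/22.4 = 1.35, against azacitidine.

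**Masking.** The table shows 22.4% both for h = 0.6 with a 4-month median and for h = 0.3 with an 8-month median. A doubled rate in an arm treated half as long is invisible in the crude percentage.

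**Fixed exposure.** With every subject treated for the same time T, the proportion is 1 - exp(-hT). At h = 0.2 per year, 6 versus 12 months gives 9.5% versus 18.1% (ratio 0.52), and 9 versus 12 months gives 13.9% versus 18.1% (ratio 0.77).

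**Does the SAP 11.1 rate correct it?** That rate is 100 x subjects with an event / at-risk time, with time stopped at the first event. At h = 0.3 it is 0.1261 / 0.4203 = 0.30 per year for the 4-month median and 0.1779 / 0.5930 = 0.30 for the 6-month median. Both arms therefore show 30 per 100 person-years. At h = 0.6 both show 60. The equality depends on a roughly constant hazard.

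**The case against.** **Much of the protection is already planned.** A reader might infer that bleeding gets no time-adjusted output and that harm could go unseen. The documents do not support that. Hemorrhagic events are a special-interest category in SAP 11.1.2, with an exposure-adjusted table. All, serious, Grade 3 or 4, fatal and treatment-ending special-interest events are also tabulated by the cycle groups of SAP 11.1.1. Adverse events are collected to 28 days after the last dose or the last visit, whichever is longer, and treatment duration and number of cycles are summarised by arm. This stands, and it makes the gap narrow. It does not close it: the category groups MedDRA terms, while 10.2.16 requires an intracranial or retroperitoneal site, more than 2 units transfused, or a hemoglobin fall of more than 2 g/dL.

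**The summary matches the declared endpoint and is descriptive.** True. SAP 10.2 confines alpha control to the primary and key secondary endpoints, and no test of bleeding is planned. The crude proportion should stay.

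**Direction.** Protocol 1.4.1 reports a death imbalance and says that most azacitidine deaths came in the first 56 days. It is tempting to conclude that azacitidine exposure is shorter and that the crude table flatters it. The documents do not establish this. They give no exposure by arm, and stopping at Cycle 6 for no benefit, or for lack of efficacy or progression, could shorten placebo exposure instead.

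**Assessment frequency.** One might add that the thinning visit schedule misses bleeds. For an intracranial bleed or one needing more than 2 units this is weak, because each visit asks about all bleeding events. Only the hemoglobin-fall component plausibly depends on sampling density.

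**Conclusion.** The point holds in a limited form. The only summaries planned under the 10.2.16 definition are crude, and the observation window is each subject's own treatment period. If time on treatment differs between arms, the comparison is distorted, in a direction set by which arm stops earlier. Under the assumed equal hazards the apparent ratio is 0.71 to 0.74 for medians of 4 versus 6 months and 0.56 to 0.61 for 4 versus 8 months. It is 1.0 when exposure is equal.

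These figures rest on assumed constant hazards and exponential treatment times. They do not estimate the bias in this trial, whose size and direction cannot be found from the documents. The consequence is a by-arm table that may mislead, not a type I error problem. The change is worth making because the SAP already uses the needed method for other safety outcomes.

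**What to change.** Keep the crude proportion as the declared endpoint and add to SAP 10.2.16, by arm in the safety population:

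1. The first-event rate per 100 person-years, using the SAP 11.1 formula with the 10.2.16 definition. At-risk time should run from first dose to first event, the Treatment Discontinuation visit or death, whichever is earliest. SAP 11.1 runs to last dose plus 28 days, which does not match the period in which bleeding is assessed.
2. The total-event rate per 100 person-years over the same assessment period, not stopped at the first event, with a 95% CI that allows for repeated events within a subject, for example by robust variance.
3. Because a single rate assumes a roughly constant hazard, either the rates by the cycle groups of SAP 11.1.1 or a cumulative incidence of first bleed with death and treatment discontinuation as competing events. The cycle-group rates address exposure more directly: the cumulative incidence shows timing, but its final level still depends on how fast subjects leave treatment.

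The cost is a small amount of programming and one derived at-risk variable. No new data are needed. Protocol Amendment 6.0 records that the primary clinical study report is already final, so the addition would now be issued as a labelled supplementary table.
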